5.3.3 Thrombocytopenia

Thrombocytopenia is a disorder in which there is an abnormally low platelet count; a normal platelet count ranges from 150,000 to 450,000 platelets per μL . The 3 major causes of low platelet counts include: (1) insufficient platelet synthesis in the bone marrow; (2) increased breakdown of platelets in the bloodstream; and (3) increased breakdown of platelets in the spleen or liver. General symptoms of thrombocytopenia include bleeding in the mouth and gums, bruising, nosebleeds, and petechiae (pinpoint red spots/rash). Severe bleeding is the

major complication, which may occur in the brain or gastrointestinal tract. Drug-induced thrombocytopenia is a reversible form of thrombocytopenia that should be suspected in a subject who presents with new onset thrombocytopenia or recurrent episodes of acute thrombocytopenia, without an obvious alternative etiology. It is commonly induced by drug dependent antibodies that cause platelet destruction or clearance by the reticuloendothelial system (drug-induced immune thrombocytopenia), and less commonly by drug-induced bone marrow suppression or autoimmune thrombocytopenia that is initiated by exposure to the offending drug but persists in its absence. The initial approach to the subject with suspected drug-induced thrombocytopenia involves confirming thrombocytopenia, establishing a temporal relationship to a drug, and eliminating other causes of thrombocytopenia. The diagnosis is made clinically by documenting prompt resolution of thrombocytopenia after discontinuation of the suspected drug (typically within 1 week). Most subjects with drug-induced thrombocytopenia require no specific treatment, as their platelet counts will recover promptly following withdrawal of the causative agent. See Section 5.5 for recording AEs.

5.4 Definition of New Onset Chronic Disease

An NOCD is a newly diagnosed medical condition that is of a chronic, ongoing nature. It is observed after receiving the investigational product and is assessed by the investigator as medically significant. Examples of NOCDs include, but are not limited to diabetes, autoimmune disease (eg, lupus, rheumatoid arthritis), and neurological disease (eg, epilepsy). Events that would not be considered as NOCDs are mild eczema, diagnosis of a congenital anomaly present at study entry, or acute illness (eg, upper respiratory infection, otitis media, bronchitis). See Section 5.5 for recording AEs.

5.5 Recording of Adverse Events

AEs, including SAEs, AESIs, and NOCDs, will be recorded on the eCRF using a recognized medical term or diagnosis that accurately reflects the event. These events will be assessed by the investigator for severity, relationship to the investigational product, possible etiologies, and whether the event meets criteria of an SAE and therefore requires immediate notification to MedImmune (see Section 5.6). See Section 5.2 for the definition of SAEs and Appendix A for guidelines for assessment of severity and relationship.

If an AE evolves into a condition that meets the regulatory definition of “serious,” it will be reported on the SAE Report Form.

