5 ASSESSMENT OF SAFETY

5.1 Definition of Adverse Events

An adverse event is the development of any untoward medical occurrence in a subject or clinical study subject administered a medicinal product and which does not necessarily have a

causal relationship with this treatment. An AE can therefore be any unfavorable and unintended sign (eg, an abnormal laboratory finding), symptom (eg, nausea, chest pain), or disease temporally associated with the use of a medicinal product, whether or not considered related to the medicinal product.

The term AE is used to include both serious and non-serious AEs and can include a deterioration of a pre-existing medical occurrence. An AE may occur at any time even if no study treatment has been administered.

Elective treatment or surgery or preplanned treatment or surgery (that was scheduled prior to the subject being enrolled into the study) for a documented pre-existing condition that did not worsen from baseline is not considered an AE (serious or nonserious). An untoward medical event occurring during the prescheduled elective procedure or routinely scheduled treatment should be recorded as an AE or SAE.

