3.7 Safety Analyses

All safety analyses will be conducted on as-treated population.

For each season as well as the two consecutive seasons combined (ie, Season 1, Season 2, Season 1 + Season 2) the summaries will be provided using the respective as-treated population. The Season 1 summaries will also be provided for each cohort (pre-term, CHD/CLD).

For each season, all safety analyses planned will be presented. For Season 1 + Season 2, number and percentage of subjects with treatment-emergent adverse events (TEAEs), treatment-emergent serious adverse events (TESAEs), adverse events of special interest (AESIs), IP-related skin reactions, and new onset chronic diseases (NOCDs) will be summarized by MedDRA System Organ Class (SOC) and Preterm Term (PT) for palivizumab/palivizumab and MEDI88987/MEDI8897 groups. The Season 1 + Season 2 summaries will be presented for CLD/CHD cohort, for CLD subjects and CHD subjects, separately.

For Season 2 summaries and Season 1 + Season 2 summaries, direct comparison between MEDI8897/MEDI8897 with palivizumab/palivizumab groups are subject to potential bias if the dropouts of Season 1 are associated with safety.

 Table 3
 Reporting Period of Treatment-emergent Adverse Events

Reporting Period	Definition of Treatment-emergent AEs	
Season 1	Any AEs that started on/after date of 1 st dose of Season 1, and prior to the end of Season 1, Day 361 or the last day prior to 1 st dose of Season 2, whichever comes earlier.	
Season 2	Any AEs that started on/after date of 1st dose of Season 2 and prior to the end of Season 2, Day 361.	
Season 1 + Season 2	Any AEs that started on/after date of 1st dose of Season 1 and prior to the end of Season 2, Day 361.	

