3.7.1 Adverse Events and Serious Adverse Events

Adverse events and serious adverse events will be coded by MedDRA version 22 or higher and the type, incidence, severity and relationship to study investigational product will be summarized by treatment group. Specific AEs will be counted once for each subject for calculating percentages. In addition, the total number of AEs will also be provided. In addition, if the same AE occurs multiple times within a particular subject, the highest severity and level of relationship observed will be reported. All treatment-emergent AEs (TEAEs) and treatment-emergent SAEs (TESAEs) occurring through Day 361 will be summarized overall, as well as categorized by MedDRA SOC and PT. In addition, the TEAEs occurring at 1% or higher in either treatment group will be reported by PT.

Nontreatment-emergent AEs/serious adverse events (SAEs), defined as AEs/SAEs that occur prior to the administration of investigational product, or after Day 361, Season 1 for preterm cohort, or after Day 361, Season 1 and prior to Day 1, Season 2 for CHD/CLD cohort, or after Day 361, Season 2 for CHD/CLD cohort, or pre-planned surgeries that are coded with PT "Cardiac Operation" and occur during the study for CHD subjects will be presented in the listings.

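### SAP Table 3 defines treatment-emergent AEs by start date only, so an ongoing AE that worsens or becomes serious after a season's first dose can be counted in the wrong season, or only listed

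*Protocol*

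**What the plan says.** SAP 3.7, Table 3, has one row per reporting period, and each row tests only when the AE started.

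- Season 1: from the first Season 1 dose "and prior to the end of Season 1, Day 361 or the last day prior to" the first Season 2 dose, whichever is earlier.
- Season 2: "Any AEs that started on/after date of 1st dose of Season 2 and prior to the end of Season 2, Day 361".
- Both seasons: "Any AEs that started on/after date of 1st dose of Season 1 and prior to the end of Season 2, Day 361".

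The two-season summary is produced "for palivizumab/palivizumab and MEDI88987/MEDI8897 groups". The second label is evidently MEDI8897/MEDI8897. The palivizumab/MEDI8897 group is not in it.

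SAP 3.7.1 sends non-treatment-emergent events to listings. These are "defined as AEs/SAEs that occur prior to the administration of investigational product" and, for the CLD/CHD cohort, also those falling after Season 1 Day 361 and before Season 2 Day 1. For repeated events it says that "if the same AE occurs multiple times within a particular subject, the highest severity and level of relationship observed will be reported".

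On recording, Protocol 5.1 says an AE "can include a deterioration of a pre-existing medical occurrence". Protocol 5.5 says "If an AE evolves into a condition that meets the regulatory definition of" serious, it goes on the SAE Report Form. Protocol 5.6 has site staff mark an AE as serious in the data capture system. Protocol 5.5.5 has examination findings that are aggravated relative to baseline reported as AEs. Protocol 5.5.1 starts AE collection at consent.

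**The concern.** TEAEs and TESAEs are part of the primary endpoint (Protocol 2.1). Protocol 5.5 and 5.6 read most naturally as one continuing AE record to which a form or a flag is added. A rule that looks only at the start date then places the event by when it began, whatever happened after dosing.

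This matters most at Season 2 Dose 1. The CLD/CHD children have chronic disease and bring up to a year of Season 1 AEs with them, and about 50 of them change drug at that point. A condition that was ongoing before re-dosing and turns serious afterwards is an event a Season 2 safety table should show.

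**Working it through.** **1. The plan's own safety figure.** Protocol 4.8.2 uses 600 children on MEDI8897 and a true rate of 0.5%.

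- P(at least one event) = 1 − 0.995^600 = 0.9506, which agrees with the stated 95%.
- One-sided 95% bound with no events = 1 − 0.05^(1/600) = 0.498%, which agrees with the stated limit of 0.5%.

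Both figures reproduce and are not in dispute. They take for granted that every event of interest in an exposed child is counted.

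**2. Three cases traced through the text, assuming the AE keeps its record and start date.**

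- (a) *Starts between consent and Season 1 Dose 1, worsens after the dose.* Table 3 excludes it from Season 1 and from the two-season row. SAP 3.7.1 leaves it in a listing. Screening can open at Day −30 (Protocol 4.2.1), but exclusion criterion 1 bars acute illness in the 7 days before randomization, which limits this case.
- (b) *Starts in Season 1, becomes serious after Season 2 Dose 1.* It fails the Season 2 row and meets the Season 1 row. Being now serious, it can appear as a Season 1 TESAE. The acute-illness exclusion gives no protection here: the Season 2 schedule (Protocol Table 6) has no eligibility check, and SAP 3.4.1 treats eligibility as not applicable to Season 2.
- (c) *Starts after Season 1 Day 361 and before Season 2 Day 1.* It fails both single-season rows, and SAP 3.7.1 only lists it. The two-season row of Table 3 would count it, so the two sections disagree. The case does not arise where the two visits coincide, as Protocol Table 5 allows.

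The highest-severity rule in SAP 3.7.1 does not help. It deals with repeated occurrences, not with one AE that changes, and it does not mention a season's first dose.

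**3. Which group can be affected, and how.**

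- Palivizumab/MEDI8897, about 50 children: under (b), an event that turned serious after MEDI8897 can be counted under Season 1 palivizumab. The group is not in the two-season summary, so no combined table recovers it.
- MEDI8897/MEDI8897, about 200, and palivizumab/palivizumab, about 50: under (b), the season can be wrong but the drug is the same, and the two-season summary still counts the event.

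**4. Scale.** The documents give no rate of AEs that worsen across a first dose, so the effect cannot be computed. What can be shown:

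- One child is 1/50 = 2 percentage points in the switch group and 1/200 = 0.5 points in the MEDI8897/MEDI8897 group.
- In 50 children, the chance of seeing a 0.5% event at all is 1 − 0.995^50 = 22%, even with full counting.
- Assumption, for illustration: if 1% to 5% of children have an AE ongoing at Season 2 Dose 1 that later worsens, that is 50 × 0.01 = 0.5 to 50 × 0.05 = 2.5 children in the switch group, and 2 to 10 in the group of 200.
- Assumption, for case (a) only: if 5%, 10% or 20% of children with the event were left in listings, 1 − (1 − 0.005 × (1 − m))^600 gives 94.3%, 93.3% or 91.0% in place of 95.1%. The zero-event bound, 0.498%/(1 − m), becomes 0.52%, 0.55% or 0.62%.

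The Phase 2b TESAE rates (Protocol 1.4.1) cannot fill the gap. Applied to 50 children, 10.4% and 16.7% give 5.2 and 8.4 children. But they come from healthy preterm infants in a first season, the higher one is the placebo rate, and neither says how many events cross a dosing date.

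**The case against.** The best counter-argument is that the misplacement is conditional. Protocol 5.5 asks for an SAE form and says nothing either way about a new AE record. Recording follows eCRF instructions (Protocol 6.4) that are not part of these documents. Protocol 5.1 and 5.5.5 allow a deterioration to be an AE in its own right, and one recorded that way has its own start date, so Table 3 places it correctly. CLD and CHD themselves pre-date enrollment, so their deterioration after re-dosing fits Protocol 5.1 directly. This stands as a limit on certainty. It does not close the gap, because no text requires an AE already on record and ongoing to get a new date when it worsens. Sites may therefore differ.

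A reader might also infer more than the documents support:

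- *That every such event is misallocated.* This depends on the unstated recording convention.
- *That the whole CLD/CHD cohort risks attribution to the wrong drug.* Only the switch group does.
- *That many pre-dose AEs are lost in Season 1.* The 7-day exclusion, and dosing on the day study drug is assigned (Protocol 4.6.1), leave little room.
- *That a change in Season 1 counts after the primary analysis shows the defect.* That analysis is cut when all children have reached Day 151, while Season 1 TEAEs run to Day 361, so later change is expected anyway.

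Safety oversight is not lost either. SAEs are reported within 24 hours whatever their onset, non-treatment-emergent SAEs are listed, and the monitoring committee reviews safety data. There is no hypothesis test, and SAP 3.7 already warns of possible bias when the MEDI8897/MEDI8897 and palivizumab/palivizumab groups are compared. The point concerns the summary tables, not the detection of events.

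**Conclusion.** The gap is real and worth correcting, though its effect is conditional. Table 3 has no clause for worsening or for becoming serious, and the protocol only partly makes up for this. Where the existing record and start date are kept, primary-endpoint events can be left in listings or counted in Season 1 when they became serious in Season 2. The consequence is sharpest in the palivizumab/MEDI8897 group, where the drug can be wrong as well as the season and no two-season summary corrects it. One child there is 2 percentage points. In the other two groups, the risk for Season 1-onset AEs is the wrong season only. The total effect is unknown. This conclusion rests on reading Protocol 5.5 and 5.6 as keeping a single record, which is the natural reading but is not stated.

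**What to change.** - **SAP Table 3.** For each period, define a treatment-emergent AE as one that started, or that increased in grade or became serious, on or after the first dose of that season (Season 1 Dose 1 for the two-season row). Use the date of worsening, or the date the event became serious, where recorded.
- **eCRF instructions.** State that such a change in an AE ongoing at a season's Dose 1 is captured with its own date. The Season 1 tables can then show grade and seriousness as they stood before Season 2 Dose 1.
- **SAP Table 3 and 3.7.1.** Make the two-season row and the non-treatment-emergent definition agree on AEs that start in the gap between seasons.

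The cost is SAP wording, one eCRF instruction, and a few extra or re-queried AE records. Some conditions will appear in both seasons. Change dates may be incomplete for records entered before the instruction, and the report should say so.

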5.5.1 Time Period for Collection of Adverse Events

AEs and SAEs will be recorded from the time of signature of informed consent through the follow-up period (Day 361).

All AESIs and NOCDs will be recorded from the time of dosing with study drug through the follow-up period (Day 361).

5.5.2 Follow-up of Unresolved Adverse Events

Any AEs that are unresolved at the subject's last visit in the study are followed up by the investigator for as long as medically indicated, but without further recording in the eCRF. MedImmune retains the right to request additional information for any subject with ongoing AE(s)/SAE(s) at the end of the study, if judged necessary.

5.5.3 Deaths

All deaths that occur during the study, including the protocol-defined follow-up period must be reported. Deaths with an unknown cause should always be reported as an SAE. A post-mortem (autopsy) may be helpful in the assessment of the cause of death, and if performed a copy of the post-mortem results should be forwarded to MedImmune representative(s) within the usual timeframes (refer to Section 5.6 for additional information).

5.5.4 Adverse Events Based on Signs and Symptoms

All AEs spontaneously reported by the care provider or reported in response to the open question from the study site staff: *'Has the child had any health problems since the previous visit?'*, or revealed by observation will be collected and recorded in the eCRF. When collecting AEs, the recording of diagnoses is preferred (when possible) to recording a list of signs and symptoms. However, if a diagnosis is known and there are other signs or symptoms that are not generally part of the diagnosis, the diagnosis and each sign or symptom will be recorded separately.

5.5.5 Adverse Events Based on Examination and Tests

An abnormal laboratory finding that requires medical intervention by the investigator, or a finding judged by the investigator as medically significant should be reported as an AE. If clinical sequelae are associated with a laboratory abnormality, the diagnosis or medical condition should be reported (eg, renal failure, hematuria) not the laboratory abnormality (eg, elevated creatinine, urine red blood cell increased)

If deterioration in a laboratory value/vital sign is associated with clinical signs and symptoms, the sign or symptom will be reported as an AE and the associated laboratory result/vital sign will be considered as additional information. Wherever possible the reporting investigator uses the clinical, rather than the laboratory term (eg, anemia versus low hemoglobin value). In the absence of clinical signs or symptoms, clinically relevant deteriorations in non-mandated parameters should be reported as AE(s).

Any new or aggravated clinically relevant abnormal medical finding at a physical examination as compared with the baseline assessment will be reported as an AE.

5.6 Reporting of Serious Adverse Events

All SAEs have to be reported, whether or not considered causally related to the investigational product, or to the study procedure(s). All SAEs will be recorded in the eCRF.

If any SAE occurs in the course of the study, then investigators or other site personnel must inform the appropriate sponsor representative(s) within 1 day, ie, immediately but **no later than 24 hours** after becoming aware of the event.

The designated study representative works with the investigator to ensure that all the necessary information is provided to the sponsor's patient safety data entry site within 1 calendar day of initial receipt for fatal and life-threatening events and within 5 calendar days of initial receipt for all other SAEs.

For fatal or life-threatening AEs where important or relevant information is missing, active follow-up is undertaken immediately. Investigators or other site personnel inform sponsor representatives of any follow-up information on a previously reported SAE within 1 calendar day, ie, immediately but **no later than 24 hours** after becoming aware of the event.

Once the investigators or other site personnel indicate an AE is serious in the electronic data capture (EDC) system, an automated email alert is sent to inform the designated sponsor representative(s).

If the EDC system is not available, then the investigator or other study site personnel reports an SAE to the appropriate sponsor representative by telephone. The sponsor representative will advise the investigator/study site personnel how to proceed.

5.7 Other Events Requiring Immediate Reporting

5.7.1 Overdose

An overdose is defined as a subject receiving a dose of investigational product in excess of that specified in the IB, unless otherwise specified in this protocol.

- An overdose with associated AEs is recorded as the AE diagnosis/symptoms on the relevant AE modules in the eCRF and on the Overdose eCRF module.
- An overdose without associated symptoms is only reported on the Overdose eCRF module.

If an overdose on a MedImmune investigational product occurs during the course of the study, then the investigator or other site personnel should inform appropriate sponsor representatives immediately, but **no later than 24 hours** after becoming aware of the event.

The designated sponsor representative works with the investigator to ensure that all relevant information is provided to the sponsor's Patient Safety data entry site.

For overdoses associated with an SAE, the standard reporting timelines apply; see Section 5.6. For other overdoses (ie, those not associated with an AE or SAE), reporting must occur within 30 days.

5.7.2 Medication Error

For the purposes of this clinical study, a medication error is an unintended failure or mistake in the treatment process for a MedImmune study drug that either causes harm to the subject or has the potential to cause harm to the subject.

A medication error is not lack of efficacy of the drug, but rather a human- or process-related failure while the drug is in control of the study site staff or subject.

Medication error includes situations where an error:

- Occurred
- Was identified and intercepted before the subject received the drug
- Did not occur, but circumstances were recognized that could have led to an error

Examples of events to be reported in clinical studies as medication errors:

- Dispensing error, eg, medication prepared incorrectly, even if it was not actually given to the subject
- Drug not administered as indicated, eg, wrong route or wrong site of administration
- Drug not stored as instructed, eg, kept at room temperature when it should be in the refrigerator
- Wrong subject received the medication (excluding IWRS errors)
- Wrong drug administered to subject (excluding IWRS errors)

Examples of events that **do not** require reporting as medication errors in clinical studies:

- Errors related to or resulting from IWRS - including those which lead to one of the above listed events that would otherwise have been a medication error
- Accidental overdose (will be captured as an overdose)

Medication errors are not regarded as AEs but AEs may occur as a consequence of the medication error.

If a medication error occurs in the course of the study, then the investigator or other site personnel informs the appropriate MedImmune representatives within 1 day, ie, immediately but **no later than 24 hours** of when he or she becomes aware of it.

The designated MedImmune representative works with the investigator to ensure that all relevant information is completed within 1 or 5 calendar days if there is an SAE associated with the medication error (see Section 5.6) and within 30 days for all other medication errors. Medication errors should be reported using a Medication Error Report Form.

